### ***Overview of TEAEs***

An overview of TEAEs including the number (%) of patients with the following events will be provided:

- Treatment-emergent adverse event (TEAE)
- Grade 3-5 TEAE
- Drug-related TEAE
- Grade 3-5 drug-related TEAE
- Serious TEAE
- Drug-related serious TEAE
- TEAE leading to death
- TEAE leading to permanent treatment discontinuation
- AESI
- Grade 3-5 AESI
- Infusion associated reaction (excluding symptoms)
- Grade 3-5 infusion associated reaction (excluding symptoms)

### ***Display of adverse events***

- All TEAEs by PT presented by all grades and grade $\geq 3$ .
- All TEAEs by primary SOC and PT presented by all grades and grade $\geq 3$ . SOC will be sorted by internationally agreed order. PT will be sorted by decreasing order of frequency,

- All TEAEs by primary SOC, HLT, HLT and PT, showing number (%) of patients with at least 1 treatment-emergent adverse event sorted by the SOC internationally agreed order. The other levels (HLT, HLT and PT) will be presented in alphabetical order.
- All drug-related TEAEs by PT presented by all grades and grade $\geq 3$ .
- All drug-related TEAEs by primary SOC and PT presented by all grades and grade $\geq 3$ .

***Deaths, serious adverse events, adverse events leading to withdrawal, and other significant adverse events***

- Death: see [Section 2.4.5.2](#).
- Serious adverse events
  - All serious TEAEs by PT presented by all grades and grade $\geq 3$ .
  - All serious TEAEs by primary SOC and PT, showing the number (%) of patients with at least 1 treatment-emergent adverse event.
  - All drug-related serious TEAEs related to isatuximab, by primary SOC and PT, showing the number (%) of patients with at least 1 treatment-emergent adverse event.
  - Listing of serious AEs.
- TEAEs leading to treatment discontinuation
  - Summary of TEAEs leading to treatment discontinuation by SOC and PT. If the number of patients who discontinued treatment due to a TEAE is  $\leq 5$ , no summary table will be provided. Instead, listing(s) will be provided.

Other significant adverse events, including IARs, respiratory TEAEs, hematological adverse events, TEAE leading to dose modification, other AESI, pre- and post-treatment AE).

- IAR-AESI (using the CMQ corresponding to the generic term of infusion related reaction reported by investigator as an AESI):
  - Analysis by patient: number of patients (used as denominator), worst grade by patient, number of episodes by patient (only 1 episode,  $\geq 1$  episode,  $\geq 2$  episodes, .... - an episode corresponds to a unique AE reference ID), first occurrence of IARs, patients with IAR at the first and/or subsequent isatuximab infusion, and number (%) of patients with at least 2 episodes of IARs at the same infusion.
  - Analysis by infusion: number of infusions (used as denominator), worst grade by infusion (a patient can have several IAR episodes at the same infusion).
  - Analysis by episode: number of episode (used as denominator), proportion of IARs occurring at each infusion, IAR duration, and day of onset.
- IAR-AESI including symptoms as reported by investigator
  - Summary of IAR-AESI by SOC and PT,
  - Listing of IAR-AESI
- Respiratory TEAEs:

- Lower respiratory TEAEs analyzed by IAR status (IAR or Non-IAR).
- Respiratory infection TEAEs analyzed by IAR status (IAR or Non-IAR).

In addition, late respiratory adverse events (i.e., occurring, worsening or becoming serious more than 30 days after last dose) will be analyzed as part of the post-treatment AEs analysis.

- Hematological abnormalities (including analysis of both AE and laboratory neutropenia):
  - Number (%) of patients with neutropenia (from laboratory abnormalities) neutropenic infections and febrile neutropenia (from AE CMQs) by grade.
- Summary of TEAEs leading to dose interruption of isatuximab, summary of TEAEs leading to dose reduction (if any), summary of TEAEs leading to dose delay.
- Pregnancy and overdose being part of the AESIs, will be listed if observed.

#### **2.4.5.2 Deaths**

Number (%) of patients who died by study period (on-treatment and post-treatment) and within 60 days from first dose of study treatment, and cause of death will be summarized. A listing of patients who died while participating in the study including cause of death, death date and days from first and last dose to death, preferred term, and causal relationship to isatuximab will be provided.

#### **2.4.5.3 Analyses of laboratory variables**

Each laboratory test result will be graded by NCI CTCAE (version 4.03), when applicable. Sponsor generic ranges are used for the grading of laboratory results, otherwise site ranges are used. For patients with multiple occurrences of the same laboratory variable during the on-treatment period, the maximum grade (worst) per patient will be used.

The number (%) of patients with abnormal laboratory tests at baseline and during the on-treatment period will be presented by all grades and each grade. At baseline, the last available value before or on the date of first study treatment administration (excluding repeated tests) will be used.

Shift tables showing the number of patients in each grade at baseline by worst grade during the on-treatment period will be provided for selected laboratory tests.

For creatinine clearance in mL per minute using MDRD formula (Revised equations for eGFR in Japanese), the number (%) of patients by category (<15, [15-30[, [30-60[, [60-90], >90) and by period (baseline and on-treatment) as well as a shift table will be provided.

#### **2.4.5.4 Analyses of vital sign variables**

The incidence of potentially clinically significant abnormalities (PCSAs) ([Table 6](#)) at any time during the on-treatment period will be summarized.

**Table 6 - Potentially clinically significant abnormalities criteria for vital signs**

Parameter	PCSA	Comments
HR	$\leq 50$ bpm and decrease from baseline $\geq 20$ bpm $\geq 120$ bpm and increase from baseline $\geq 20$ bpm	To be applied for all positions (including missing) except STANDING.
SBP	$\leq 95$ mmHg and decrease from baseline $\geq 20$ mmHg $\geq 160$ mmHg and increase from baseline $\geq 20$ mmHg	To be applied for all positions (including missing) except STANDING.
DBP	$\leq 45$ mmHg and decrease from baseline $\geq 10$ mmHg $\geq 110$ mmHg and increase from baseline $\geq 10$ mmHg	To be applied for all positions (including missing) except STANDING.
Weight	$\geq 5\%$ increase from baseline $\geq 5\%$ decrease from baseline	FDA Feb 2007.

Temperature and respiratory rate will be summarized at baseline and end of treatment.

A listing of vital signs will be provided.

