9. Isatuximab Safety Labs: Should a isatuximab infusion associated reaction of Grade ≥ 2 occur, additional blood sampling during the AE is required for analysis of markers of potential tumor lysis syndrome (uric acid, lactate dehydrogenase [LDH], BUN, creatinine, potassium, phosphate, ionized or corrected calcium).
10. Physical Examination: Consists of examination of major body systems including neurological, digestive, extramedullary myeloma localizations, respiratory, hepatomegaly, splenomegaly, lymphadenopathy. Only clinically relevant findings will be reported in the electronic case report form (e-CRF) as AEs.
11. Vital Signs: Heart rate (HR), temperature, respiratory rate (RR), blood pressure (BP) to be taken pre-infusion, mid-infusion (when half the volume is administered), and end-infusion on days of investigational medicinal product (IMP) administration. If the infusion rate changes because of an infusion-associated reaction, vital signs should be monitored every hour and at the end of the infusion.
12. 12-Lead ECG, 2-D Echocardiogram or Multigated Acquisition (MUGA): To be performed at screening and then as clinically indicated (the same methods must be used throughout the study). LVEF need to be checked for eligibility.
13. Hematology includes: Hemoglobin, hematocrit, RBC, WBC with differential, Mean Corpuscular Volume (MCV) and platelet counts. To be done at screening, then prior to pre-medication and IMP administration on Day 1, Day 8, Day 15 and Day 22 of Cycle 1 and on Day 1 and Day 15 of every subsequent cycle, at the EoT visit and as clinically indicated. If Grade 4 neutropenia, assess ANC every 2-3 days until ANC $\geq 0.5 \times 10^9/L$ and at least weekly thereafter until ANC $\geq 1.0 \times 10^9/L$. Perform direct and indirect coombs tests prior to the first IMP administration.
14. Not required to be repeated prior to Day 1 Cycle 1 if the screening labs were performed within 3 days prior to first IMP administration.

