13.4.4.5 Vital signs

The descriptive statistics (including mean, median, SD, minimum and maximum) of all vital signs' variables (raw data and changes from baseline) will be calculated for each visit or study endpoint (baseline, each post baseline time point, last on treatment value and/or worst value) by dosing levels.

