#### **2.4.5.4 Analyses of vital sign variables**

The summary statistics (including number, mean, median, standard deviation, minimum, and maximum) of all vital signs variables will be calculated for each planned visit (pre-infusion, mid-infusion and end-infusion for cycle 1 to cycle 3) by dose level cohort.

The incidence of potentially clinically significant abnormalities (PCSAs) at any time during the on-treatment period will be summarized by dose level cohort.

The PCSA values are defined as abnormal values considered medically important by the Sponsor according to predefined criteria/thresholds based on literature review and defined by the Sponsor for vital signs. PCSA criteria will determine which patients had at least 1 PCSA during the on-treatment period, taking into account all evaluations performed during the on-treatment period, including nonscheduled or repeated evaluations (Appendix A).

A listing of vital signs will be provided.

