## 2 STATISTICAL AND ANALYTICAL PROCEDURES

### 2.1 ANALYSIS ENDPOINTS

#### 2.1.1 Demographic and baseline characteristics

The baseline value is defined as the last available value before the first isatuximab administration, unless otherwise specified.

All baseline safety and efficacy parameters (apart from those listed below) are presented along with the on-treatment summary statistics in the safety and efficacy sections ([Section 2.4.5](#) and [Section 2.4.4](#)).

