#### **2.1.4.4 Vital signs variables**

Vital signs include: heart rate, respiratory rate, temperature, body weight, and systolic/diastolic blood pressure.

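### The Phase 2 SAP summarises vital signs less fully than protocol 13.4.4.5 plans: temperature and respiratory rate only at baseline and an undefined end of treatment, and no change from baseline for any sign

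*SAP*

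**What the plan says.** **Planned analysis.** Protocol 13.4.4.5 plans mean, median, SD, minimum and maximum for every vital sign: "raw data and changes from baseline) will be calculated for each visit or study endpoint". The occasions it then names are baseline, every later time point, the final on-treatment value and/or the worst value. Protocol 13.4 applies these methods to both phases unless something else is specified.

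**Collection.** Footnote 11 in protocol 1.6 says vital signs are "to be taken pre-infusion, mid-infusion (when half the volume is administered), and end-infusion on days of investigational medicinal product (IMP) administration". They are taken hourly if the rate is changed because of an infusion reaction.

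**Phase 2 SAP.** Section 2.1.4.4 defines the set: "Vital signs include: heart rate, respiratory rate, temperature, body weight, and systolic/diastolic blood pressure". Section 2.4.5.4 then provides three things:
- the incidence of PCSAs "at any time during the on-treatment period will be summarized", with criteria in Table 6 for heart rate, systolic and diastolic blood pressure and weight only;
- for the other two signs, "Temperature and respiratory rate will be summarized at baseline and end of treatment";
- "A listing of vital signs will be provided".

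Section 2.1.1 adds: "The baseline value is defined as the last available value before the first isatuximab administration, unless otherwise specified". Section 2.5.5 allows unscheduled vital sign readings only for computing worst values or grades.

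**Phase 1 SAP.** Its section 2.4.5.4 gives summary statistics for all vital signs at "pre-infusion, mid-infusion and end-infusion for cycle 1 to cycle 3", as well as a PCSA table.

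**The concern.** Changes in vital signs are part of the secondary safety endpoint in the protocol's Clinical Trial Summary, and infusion reactions are a common known toxicity of this antibody. In protocol Table 1 (the earlier global study), infusion related reaction was reported in 9, 11, 13 and 13 patients across groups of 23, 24, 25 and 25. That is 46/97 = 47%. Appendix G lists pyrexia, dyspnea and respiratory distress among the typical symptoms.

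Temperature and respiratory rate bear directly on those symptoms. The protocol has them measured before, during and at the end of each infusion. In the larger part of the trial, the SAP summarises them at one time before treatment and one time at its end, with nothing that captures a peak during infusion. At stake is whether the report can describe how far these signs moved, as the protocol's own analysis section intends.

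**Working it through.** No sample size or error rate is involved. The check compares the texts and then counts readings.

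**1. Protocol 13.4.4.5 against Phase 2 SAP 2.4.5.4**

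| Item | Protocol | Phase 2 SAP: heart rate, blood pressure | Phase 2 SAP: temperature, respiratory rate |
|---|---|---|---|
| Descriptive statistics | All vital signs | None; PCSA counts only | Baseline and end of treatment |
| Change from baseline | Yes | Used inside the PCSA criteria, not summarised | Not mentioned |
| Readings at post-baseline time points | In the and/or list | Feed the PCSA count | Not summarised |
| Worst value | In the and/or list | Reflected indirectly in the PCSA count | Not defined |

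Weight, which the SAP counts as a vital sign, is treated like heart rate and blood pressure.

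**2. Unscheduled readings.** Phase 2 SAP 2.5.5 confines these to worst values or grades. Neither is defined for temperature or respiratory rate, so unscheduled readings of these signs enter no summary. The hourly readings taken after a rate change have no summary either, whether or not they count as unscheduled.

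**3. Meaning of end of treatment.** The SAP does not say whether this is the end-of-treatment (EoT) visit or the last on-treatment value. Protocol 12.4 places the EoT visit 30 ± 7 days after the last dose, so on days 23 to 37. The on-treatment period in Phase 2 SAP 2.1.4 ends 30 days after the last dose. A visit on days 31 to 37 is therefore outside it and could not supply a last on-treatment value.

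**4. Scheduled infusion-day readings of each of the two signs, per patient.** Inputs are 4 infusions in Cycle 1 and 2 in each later cycle (protocol 6.5), with 3 readings per infusion (footnote 11) and full dosing assumed.
- Cycles 1 to 3: (4 + 2 + 2) × 3 = 24 readings, of which (4 + 2 + 2) × 2 = 16 are mid- or end-infusion.
- Summarised: normally 1, the Cycle 1 Day 1 pre-infusion reading, which serves as baseline.
- Not summarised: 24 − 1 = 23, including all 16 mid- and end-infusion readings.
- If end of treatment means the last on-treatment value, and that value falls on an infusion day in these cycles, one more reading could enter: 24 − 2 = 22 not summarised.

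**5. Cycle 1 across Phase II.** With about 30 patients (Clinical Trial Summary), 30 × 4 × 3 = 360 scheduled readings of each sign. Taking only the 30 baseline readings as summarised, 330/360 = 91.7% are listed only.

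**6. Declared departures.** Phase 2 SAP Table 1 (section 1.5) has three entries, none on vital signs. Section 1.6 is marked not applicable because this is the first version.

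**The case against.** The strongest reply is that the protocol list is joined by and/or, is introduced as visits or study endpoints, and includes both baseline and the last on-treatment value. A summary at baseline and end of treatment arguably fits it. This stands in part: a reader might infer that the protocol commits to every time point or to the worst value, and the wording does not go that far. It does not rescue the section. Change from baseline is planned without such latitude and is missing, heart rate and blood pressure have no descriptive statistics at all, and end of treatment may not be an on-treatment value.

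The second reply is that infusion reactions are analysed directly. Phase 2 SAP 2.1.4.1 and 2.4.5.1 plan analyses of reactions reported as adverse events of special interest by patient, infusion and episode, with symptoms. They also plan tables of treatment-emergent events starting on the infusion day or the next, and respiratory events by reaction status. This stands and limits the consequence. But protocol 10.5.1 records a vital sign abnormality as an adverse event only if it is symptomatic, treated, leads to discontinuation or a dosing change, is serious, or is of special interest. Milder changes reach no table for these two signs, and event tables do not show the size of a change.

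Third, every reading is listed. That is true, but a listing is not the descriptive analysis the protocol plans.

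Three further inferences fail:
- That no reading around an infusion is summarised. The first pre-dose reading normally is, as baseline, and heart rate and blood pressure readings feed the PCSA table.
- That Phase II cannot be compared with Cohort 2. The PCSA thresholds in Phase 1 SAP Appendix A and Phase 2 SAP Table 6 are identical. Only the descriptive tables have no counterpart.
- That the Phase 1 SAP is a fully compliant model. It covers the infusion time points but does not mention change from baseline and sets no PCSA criterion for temperature or respiratory rate.

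**Conclusion.** The gap is real and its consequence modest. The Phase 2 SAP delivers less than protocol 13.4.4.5 plans for a stated secondary safety endpoint, and does not say so. The firmest shortfalls are the missing change from baseline for all vital signs and the missing descriptive statistics for heart rate and blood pressure. For temperature and respiratory rate there is also no during-infusion or worst-value summary.

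The counts rest on full dosing through Cycle 3, on the Cycle 1 Day 1 pre-infusion reading being the baseline, and, for the 330 of 360, on about 30 Phase II patients. They measure how much planned data goes untabulated. They do not measure bias or missed signals. The primary endpoint and its test are unaffected, and the documents do not support reading this as a failure to analyse infusion reactions.

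**What to change.** Amend Phase 2 SAP 2.4.5.4 in three places.

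1. Add descriptive statistics, raw and as change from baseline, for all vital signs at the Phase 1 SAP time points: pre-, mid- and end-infusion in Cycles 1 to 3. Weight is measured once per visit and would be summarised by visit.
2. Add the per-patient worst on-treatment temperature and respiratory rate, including unscheduled and hourly readings, and state which direction counts as worst. A per-patient worst value matters because visit means in a single arm of about 30 can hide individual peaks.
3. State whether end of treatment means the EoT visit or the last on-treatment value.

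If the sponsor prefers the narrower display, it should be recorded as a departure from protocol 13.4.4.5 with a reason.

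The readings are already collected, so the cost is a few extra tables. The Phase 1 SAP specifies the time points, but change from baseline and worst values go beyond it and would need their own specification.

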#### **2.4.5.5 Analyses of electrocardiogram variables**

A listing of ECG results will be provided.

#### **2.4.5.6 Analyses of other safety endpoints**

ECOG PS and results of bone lesions and chest X-ray will be listed.

The number (%) of patients with TLS reported under the TLS standard MedDRA query (SMQ) (i.e., haemorrhagic tumor necrosis, TLS, tumor necrosis) will be provided. Among those patients, the number (%) of patients with laboratory and clinical parameters which could be indicative of TLS prior to first dose and during the on-treatment period will also be provided.

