1.6 FOOTNOTES FOR STUDY FLOWCHARTS

1. Evaluation: Assessments to be performed prior to study drug administration unless otherwise indicated. Results should be reviewed by the Investigator.
2. If the patient cannot be registered within 21 days of informed consent, the same patient may be re-screened after discussion with the sponsor, provided that there are no persisting safety concerns for patient's study participation. The informed consent form will have to be re-signed by the re-screened patient before starting re-screening procedures. New patient number will be given for the re-screened patients.
3. Cycle: A cycle is 28 days.
4. Allowance for Day 8, Day15 and Day 22 at first cycle is +/- 2 days. Allowance for Day 1 and Day15 at subsequent cycles are +/- 3 days.
5. The ICF should be signed before any study-related procedures or tests are initiated.
All patients who participated in Phase I part and is going to continue study treatment after completing Cycle 1 must sign a second ICF before commencing IMP administration in Cycle 2 Day1.
6. Demography: Includes date of birth, gender and race.
Medical/Surgical History: Includes relevant history of previous/associated pathologies other than multiple myeloma.
Disease History: Includes date of initial diagnosis of symptomatic MM, subtype, stage, previous anti-MM therapy (drug name by line of therapy, start and end date of administration, reason for discontinuation, best response and date of progression/relapse), disease status at inclusion (refractory to last IMiD or PI included therapy). In addition, results of additional procedures (such as karyotype, FISH, etc) performed as part of standard of care to assess the current disease status may also be collected. A patient card will be provided to the patient indicating he/she is receiving an anti-CD38 treatment and the site will notify its blood bank that the patient is receiving an anti-CD38 treatment.
7. Hospitalization: Day 1 through the entire day of the 3rd infusion (Day 15) hospitalization is recommended. Hospitalization will be expanded to the entire first cycle of the study treatment (ie. DLT observation period), if the investigator and the study committee judged appropriate.
8. Registration process can be completed in Day -1 however all eligibility criteria should be re-confirmed by investigators in Day 1 before IMP administration.

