6.6.2 Management of Potential Tumor Lysis Syndrome

General guidelines for the management of the tumor lysis syndrome are provided in [Table 4](#).

Table 4 - Tumor lysis syndrome management

Symptom	Recommended Action
Laboratory Tumor Lysis Syndrome (LTLS): 
• ≥ 2 simultaneous abnormalities within 3 days prior to and up to 7 days after start of treatment• Uric acid >8 mg/dL (>475.8 μmol/L)• Potassium >6.0 mmol/L• Phosphorus >4.5 mg/dL (>1.45 mmol/L) Corrected calcium <7.0 mg/dL (<1.75 mmol/L) or ionized calcium <1.12 mg/dL (<0.3 mmol/L) ^a	Omit isatuximab until all serum chemistries have resolved Ensure normal hydration; correct laboratory abnormalities, fluid overload, electrolyte or acid-based deviations Monitor TLS complications including renal functions Refer to "serious adverse drug reaction countermeasure manual" for TLS treatment ^b . Reinstitute isatuximab treatment at full doses after resolution
Clinical TLS (CTLS): meeting criteria for LTLS in addition to one of the following complications, 
• Acute kidney injury: increase in the serum creatinine level of 0.3 mg/dL (26.5 μmol/L) or the presence of oliguria, defined as an average urine output of <0.5 mL/kg/hr for 6 hrs.• Seizures, cardiac dysrhythmia, neuromuscular irritability (tetany, paresthesias, muscle twitching, carpopedal spasm, Trousseau's sign, Chvostek's sign, laryngospasm, bronchospasm), hypotension, or heart failure probably or definitely caused by hypocalcemia• Dysrhythmia probably or definitely caused by hyperkaliemia	

a The corrected calcium level in milligrams per deciliter = measured calcium level in milligrams per deciliter + $0.8 \times (4 \text{-albumin in grams per deciliter})$

b Serious adverse drug reaction countermeasure manual for TLS: <http://www.mhlw.go.jp/topics/2006/11/dl/tp1122-1e17.pdf>
MHLW site: http://www.mhlw.go.jp/stf/seisakunitsuite/bunya/kenkou_iryou/iyakuhin/topics/tp061122-1.html

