10.5 OBLIGATION OF THE INVESTIGATOR REGARDING SAFETY REPORTING

10.5.1 Adverse Events

All AEs regardless of seriousness or relationship to the IMP, spanning from the signature of the informed consent form (ie, occurring during the baseline period even in the absence of any administration of IMP), up to 30 days following the last administration of study treatment, are to be recorded on the corresponding page(s) included in the e-CRF.

Whenever possible, diagnosis or single syndrome should be reported instead if symptoms. The Investigator should specify the date of onset, intensity, action taken with respect to IMP, corrective treatment/therapy given, additional investigations performed, outcome, and his/her opinion as to whether there is a reasonable possibility that the AE was caused by the IMP.

Vital signs or ECG abnormalities are to be recorded as AEs only if they are symptomatic and/or requiring corrective treatment and/or leading to treatment discontinuation and/or modification of dosing and/or fulfilling a seriousness criterion and/or is defined as an AESI (see [Section 10.5.5](#)).

Laboratory abnormalities are to be recorded as AEs only if they lead to treatment discontinuation and/or modification of dosing and/or fulfill a seriousness criterion and/or are defined as an AESI (see [Section 10.5.5](#)).

10.5.2 Serious Adverse Events, Adverse Events of Special Interest, Pregnancy and Symptomatic Overdose

In the case of a SAE, an AESI, a pregnancy report, or a symptomatic overdose, the Investigator must immediately:

- ENTER (within 24 hours) the information related to a SAE, an AESI, a pregnancy report or a symptomatic overdose in the appropriate screens of the e-CRF; the system will automatically send e-notification to the monitoring team after approval of the Investigator within the e-CRF or after a standard delay.
- There may be instances when copies of medical records for certain cases are requested by Sanofi. In such case, care should be taken to ensure that the patient's identity is protected and the patient's identifiers in the study are properly mentioned on any copy of a source document provided to the Company. For laboratory results, include the laboratory normal ranges.
- All further data updates should be recorded in the e-CRF as appropriate within 24 hours of knowledge. In addition, every effort should be made to further document each SAE that is fatal or life threatening within the week (7 days) following initial notification.

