#### **2.4.5.6 Analyses of other safety endpoints**

ECOG PS and results of chest X-ray will be listed.

The patients with TLS reported under the TLS standard MedDRA query (SMQ) will be listed.

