#### **2.1.4.6 Other safety endpoints**

Other safety endpoints include:

- Cytokines
  - TNF- $\alpha$ , IL-4, IL-6, IL-1- $\beta$ , IFN- $\gamma$
- IAR laboratory test
  - Complement (C3a, C4, CH50)
  - Serum tryptase
- Chest X-ray at baseline and as clinically indicated.
- Tumor lysis syndrome (TLS)

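### Phase 2 SAP 2.4.5.6 examines laboratory evidence of tumor lysis syndrome only in patients with a reported TLS term, so it can confirm reported cases but cannot find unreported ones

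*SAP*

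**What the plan says.** Phase 2 SAP 2.1.4.6 lists TLS among the other safety endpoints and does not define it. Section 2.4.5.6 then plans two counts. The first is patients with an adverse event term in the TLS standardised MedDRA query (SMQ), which covers haemorrhagic tumor necrosis, TLS and tumor necrosis. The second is nested in the first: "Among those patients, the number (%) of patients with laboratory and clinical parameters which could be indicative of TLS prior to first dose", and the sentence goes on to include the on-treatment period. The section names no parameters or cut-offs and does not refer to protocol Table 4.

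Protocol 6.6.2, Table 4, describes laboratory TLS from laboratory values alone. It requires at least two "simultaneous abnormalities within 3 days prior to and up to 7 days after start of treatment", drawn from uric acid, potassium, phosphorus and calcium. The action given there is "Omit isatuximab until all serum chemistries have resolved".

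On reporting, protocol 10.5.1 states: "Laboratory abnormalities are to be recorded as AEs only if they lead to treatment discontinuation and/or modification of dosing", or if they are serious or an adverse event of special interest. Section 10.5.8 is to the same effect. TLS is not on the special-interest list in protocol 10.5.5 or in Phase 2 SAP 2.1.4.1.

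The Phase 1 SAP differs. Its section 2.4.5.6 says: "The patients with TLS reported under the TLS standard MedDRA query (SMQ) will be listed", and its section 2.4.5.3 also lists every laboratory variable.

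**The concern.** A laboratory check limited to patients already flagged by an adverse event term can only corroborate. It says nothing about patients who had the laboratory pattern and no such term. The protocol gives TLS its own management table, and it requires extra blood sampling for TLS markers after an infusion reaction of Grade 2 or higher. A reader of the study report would reasonably take a TLS count of zero, or close to it, as a statement about all treated patients. As planned, the count would reflect what sites recognised and how they coded it. The laboratory data that could test this are collected, but no planned Phase 2 output uses them that way.

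**Working it through.** The documents state no TLS count or rate, so there is no planned figure to reproduce. The check is a trace of who gets counted.

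1. **What the two counts can show.** Let S be the patients with an SMQ term and L the patients with at least two simultaneous Table 4 laboratory criteria. Phase 2 SAP 2.4.5.6 reports S, and the part of S with indicative laboratory or clinical parameters. The second count cannot exceed S. If S is 0, the second count is 0 whatever L is. Patients in L but not in S appear in neither.

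2. **Who can be in L but not in S.** Under Table 4, recognised laboratory TLS leads to a held dose. Under protocol 10.5.1 and 10.5.8 an effect on dosing makes the abnormality a reportable event, and 10.5.1 prefers a diagnosis over individual findings. A case recognised and handled this way should reach S. Three routes remain: the combination was not recognised; it resolved before the next dose, so treatment was not affected; or it was reported as separate electrolyte terms.

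3. **Whether another Phase 2 output recovers them.** Section 2.4.5.3 grades each test separately and takes the worst grade per patient over the on-treatment period, which runs to 30 days after the last dose (2.1.4). A patient with high potassium in Cycle 1 and high uric acid in Cycle 5 contributes the same entries as one with both on the same day in the first week. The shift tables for selected tests have the same limit. Unlike Phase 1, section 2.4.5.3 plans no listing of all laboratory variables.

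4. **Whether the data exist.** Serum chemistry (protocol 1.6, footnote 15) includes uric acid, potassium, phosphate and corrected calcium. It is taken at screening, on Days 1, 8, 15 and 22 of Cycle 1, and on Days 1 and 15 of later cycles. Footnote 14 lets Day 1 be skipped only if screening chemistry fell within 3 days before first dose, so the schedule gives a pre-dose sample inside the Table 4 window.

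5. **The post-dose window.** Without a Grade 2 or higher infusion reaction, the only scheduled post-dose chemistry that can fall in the 7-day window is Day 8. Footnote 4 says: "Allowance for Day 8, Day15 and Day 22 at first cycle is +/- 2 days". Days 6 to 10 are therefore allowed. Day d is d − 1 days after first dose:
   - Days 6, 7, 8: 5, 6, 7 days, inside the window.
   - Days 9, 10: 8, 9 days, outside the window.

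6. **Specificity of the criteria.** Table 4 phosphorus: 4.5 mg/dL × 0.3229 = 1.45 mmol/L, as the protocol states. Phase 2 SAP Appendix A puts the upper normal limit for phosphate at 1.4 mmol/L. The gap is 1.45 − 1.40 = 0.05 mmol/L. The ionized calcium cut-off is 1.12 mg/dL × 0.2495 = 0.28 mmol/L, which the protocol rounds to 0.3, so a derivation should fix the unit it uses.

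7. **Scale.** Protocol 13.4 reports the phases separately except for efficacy, so the 33-36 pooled efficacy patients are not the safety denominator. With about 30 Phase II patients (Clinical Trial Summary), one missed patient is 1/30 = 3.3%.

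**The case against.** The strongest reply is that the protocol already captures laboratory TLS. It tells sites to hold treatment, a change to treatment makes the abnormality an adverse event, a syndrome is to be reported in preference to its parts, and investigators review all results. This stands for recognised cases. A reader might infer that all laboratory TLS outside the SMQ group goes uncounted by design; the documents do not support that, and the gap is limited to the three routes in step 2.

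Next, Table 4 is management guidance and not an endpoint definition. It sits under guidelines for handling adverse events, TLS is not among the protocol's endpoints, and protocol 13.4.4.6 plans no analysis of other safety variables. That is correct, and restricting the check to reported cases does favour specificity. But the SAP chose to make TLS an endpoint and to look at laboratory parameters without saying which, and Table 4 is the only set of criteria in the documents.

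The composite is also not very specific. Its phosphorus cut-off is barely above normal, it requires no change from baseline, and patients with eGFR down to 30 mL/min/1.73 m² are eligible. This stands, and it governs how the result should be labelled.

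A reader might also extend the criticism to Phase 1. That does not hold: Phase 1 lists all laboratory variables, and with 6 to 12 evaluable patients simultaneity can be read from the listing.

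Finally, the individual laboratory abnormalities are graded for every Phase 2 patient. They are, but separately, so the combination and its timing are lost.

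**Conclusion.** The point holds for the Phase 2 SAP. The laboratory check in 2.4.5.6 can confirm SMQ-reported cases but cannot find unreported ones, and no other planned Phase 2 output shows simultaneous abnormalities in the remaining patients. The cases at risk are those that were unrecognised, resolved before the next dose, or were reported as separate electrolyte terms.

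The size is unknown. It might be inferred that the trial will understate TLS by some fraction, or report none where cases exist. The documents give no rate of laboratory TLS and no reporting probability, so neither can be claimed. What can be said is that each missed patient is about 3.3% of about 30 Phase II patients, and that a low reported count could not be read as low occurrence. The conclusion assumes that the Phase 2 SAP as provided describes all planned Phase 2 laboratory output. The effect is on safety reporting only; the primary response-rate analysis is not affected.

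**What to change.** In Phase 2 SAP 2.4.5.6, replace the restriction to SMQ-reported patients with a derivation in all treated Phase 2 patients:

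- Flag a patient with at least two Table 4 laboratory criteria on the same sample date, using scheduled and unscheduled chemistry. Section 2.5.5 now limits unscheduled laboratory values to worst values and grades, so it needs a stated exception.
- Report n (%) pre-dose and post-dose. Take the Table 4 window (3 days before to 7 days after start of treatment) as the main count, and add a supplementary count that includes a Day 8 visit performed on Day 9 or 10.
- Cross-tabulate the flag with SMQ-reported cases, and keep the SMQ count.
- Label the result a supplementary laboratory screen, because the phosphorus cut-off lies close to the SAP's own upper normal limit.

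The Phase 1 SAP needs no change, given its full laboratory listing.

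The cost is one derived variable and one table from chemistry already collected, with no new sampling and no change to patient management. The drawback is that some mild or pre-existing laboratory-only cases will appear. The pre-dose column shows those already present before treatment, and the label guards against over-reading the rest.
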